Study Design: Interested volunteers will be screened by telephone or in person in respective clinics or via televisit and then scheduled for a screening visit (week 0). If potential participants express interest, they will be provided an email address or phone number to call for more information. Alternatively, participants will be asked if they would like to be called to receive more information and are willing to provide their contact information to study staff. If after receiving more information, the potential participant is interested, then pre-screening questions (appendix D) will be asked. If still eligible, then a screening appointment will be arranged by study staff. If the participant is not interested in participating the participant will continue standard OB care for gestational diabetes.

Study visits and intervention: Upon arriving to the pre-intervention visit, informed consent will be obtained after which a point of care HbA1c (if no HbA1c available within the last 2 weeks) will be obtained and oral glucose tolerance test (OGTT) and or HbA1c results reviewed and inclusion/exclusion criteria reviewed. At the pre-intervention session (week 0) the control group will wear CGM for 10 days blinded. The intervention group will be given CGM training and instructions and start Real Time-CGM (RT-CGM). Controls will be asked to follow their OB provider's instructions for checking blood sugar via capillary blood glucose (ie fingersticks). If no recommendations have been given, instructions will be to start checking fingersticks fasting and 1-hour post-meals, which is typical for GDM management. All participants will be asked to write their glucose levels/results in a log provided. RT-CGM participants will be asked to review their RT-CGM and write down their fasting glucose in am, prior to each meal and 1 and 2 hours post-meal. As well they will be instructed to document any sugars < 60 mg/dl seen by CGM in their log.

Participants will then follow-up at week 2 (session 2) at which time the control group will have their blinded CGM data collected and the RT-CGM group will download their CGM data and ensure CGM working appropriately. The control group will continue to monitor fingerstick blood glucose as recommended by their

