pregnancy obstetric provider. The intervention group will continue the RT-CGM device and will be instructed to continue fingersticks only when concerned for hypoglycemia and/or inaccuracy of sensor. The control and intervention groups will follow-up serially for the duration of pregnancy (see schematic for visits below). The control group will wear the blinded CGM at serial timepoints throughout pregnancy and the intervention group will have serial download of RT-CGM. Participants will also have labs checked every 8 weeks which will include HbA1C and fructosamine at beginning and end of the study. It is estimated that participants will be enrolled at 24-28 weeks and have 4 visits (estimating a pregnancy duration of 40 weeks). Some participants may receive a diagnosis of gestational diabetes earlier and thus have more sessions. Maternal and neonatal outcomes will be abstracted from delivery records.

[figure not shown]

Figure 1: Study Design Schematic: N=100 Control N=50 GDM Intevention: GDM N=50

*Approximate Total duration of CGM use would be 14-22

**see timeline for measures appendix B

Figure 2: Timeline for Visits Based on High Risk for Gestational Diabetes and Typical Risk

		Screening Visit 0	Visit 1b High risk	Visit 1a	Visit 2++	Visit 3	Visit 4*
Gestational age Intervention	High Risk	14	20-22 weeks	24-30 weeks	30-32 weeks	34-36 weeks	38-40 Weeks

Gestational age Intervention	Typical Risk	24-28	N/A	24-30 weeks	30-32 weeks	34-36	38-40 Weeks
Gestational age Control	High Risk	14	14-16 weeks	24-30 weeks	30-32	34-36	38-40 Weeks
Gestational age Control	Typical Risk	24-28	N/A	24-30 weeks	30-32 weeks	34-36	38-40 weeks

+++ visits will be a minimum of 2 weeks apart

*38-40 week data only collected in participants that make it to 38- 40 week gestational age

Screening/Pre-Intervention Visit(week 0):

Consent (appendix R) will be obtained prior to any screening procedures being completed, and conducted in a quiet room or private televisit. Participant will be given ample time to ask questions, and a copy of the signed consent form will be given prior to start of screening visit. Participants will fill out a contact form, including emergency contact. Study staff will review medical history and medications, pregnancy history, patient's mother's pregnancy history, sleep history, and lipid profile if available (appendix D), as well as all inclusion/exclusion criteria.

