Vital signs will be collected, including height, weight (current and pre-pregnancy), blood pressure, maternal resting heart rate, and estimated gestational age. Maternal ultrasound results will be reviewed if available.

Glucose tolerance test results will be reviewed. Two blood pressure and pulse readings will be taken and HbA1c, both point of care (fingerstick) and HbA1c serum and fructosamine via LabCorp will be obtained. Approximately 1 teaspoon of blood will be drawn. If a patient has an HbA1c documented in the medical record within 2 weeks of the pre-intervention session, then the point of care HbA1c will not be done. The available HbA1c will be used. If they meet all inclusion and exclusion criteria (as outlined above), they will be randomized into either the RT-CGM intervention or control arm at the screening visit.

At the pre-intervention session (week 0) the control GDM group will be asked to wear the CGM blinded for 10 days. They will be asked to continue their usual diet and activity. If, for any reason, the CGM device fails to capture at least 3 days worth of data, the subject may be asked to repeat this measurement at an unscheduled visit. The control group will be given a glucose meter (onetouch) and instructed to follow their obstetric provider's recommendations about checking glucose by meter or if they have not been given instructions or do not remember their instructions they will be asked to check sugars fasting and 1 hour after meals. They will also be given a handout that explains glucose goals and how food and activity effects glucose levels. (Appendix A1,A2). The intervention group will be given RT-CGM and instructed on use with a handout that explains glucose goals and how food and activity effects glucose levels (see handout/Appendix A). The intervention group will also be given a glucose meter (onetouch) and instructed to use for symptoms of low glucose or if they question the accuracy of the CGM. Both groups will be given standard gestational diabetes teaching and nutrition counseling by the RN in clinic and with individual nutrition appointments with the nutritionist, as per current local standard of care.

Participants will be given self-report questionnaires on physical activity, nutrition, sleep history, pregnancy history and overall wellness. Week 0 consenting and baseline data/measurements will take between 1 hour 30 minutes and 2 hours.

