study visit 2 (with de-identified data) or it sends the information via wireless radio frequency to a monitoring/display device or to a cellular phone so one can see their own data on their glucose and we can download it remotely. The device automatically generates an alert for glucose < 55, and an alert will also be generated for glucose > 140 in the unblinded portion of the study. The intervention group participants will be given a handout (Appendix K) for troubleshooting these alerts, particularly during the blinded portion of the study. DEXCOM G6 is FDA approved for use in patients with diabetes and will be used in accordance with instructions as approved for diabetes. It is not currently approved for patients with gestational diabetes but will be used in accordance with instructions as approved for diabetes. The risk is minimal with use of this device. In this study, we recommend patients connect the CGM to their cell phones, but if unable/unwilling, we will provide transmitters for participants to allow for real-time monitoring. Study staff will insert the first sensor for the groups and demonstrate how to insert additional sensors for the intervention group who will continue to use RT-CGM. If this is to be done as a televisit, the sensors, transmitter, and device (if needed) will be mail to the participant. Then the study staff will walk the participant through the first insertion through a virtual zoom visit. Patients will also have a YouTube video available for reference for the patients. For the blinded control, the research coordinator will insert all sensors unless televisit is needed with procedure as above. The patients will be instructed on how to remove the sensor themselves after 10 days and bring back their scheduled OB visit. The intervention group will wear the RT-CGM continuously and change the sensor every 10 days for the duration of the pregnancy and have telephone support and may refer to the YouTube video on insertion if needed. The intervention participants will have RT-CGM download serially over the study during regularly scheduled OB visits or televisits. The control group participants will wear the blinded CGM at beginning, at 30-32 and 34-36 weeks of the study. If, during the blinded portion of the study, due to device malfunction (rather than subject non-compliance), the device records less than 3 days of data, the participant can return to restart another 10 days of blinded CGM data.

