Perception/Satisfaction with CGM and Fingersticks/Meter (Appendices J): The Harvard Joslin Diabetes Center has developed a series of questionnaires on CGM experiences, opinions and expectations that will be given at the end of the intervention and has been adapted for the GDM. Additionally, questions about food changes and activity changes that was created for CGM use(19,20) . Questionnaires have been adapted for use in those using only meter fingersticks and for GDM.

Sleep Questionnaire (appendix Q) The Pittsburgh Sleep Questionnaire is good tool for screening sleep disorders in the population and has been used in pregnancy (22,23)

N: Glucose/CGM Data /Evaluation Measures: The compliance and duration wear for participants with CGM will also be recorded. Glucose dynamics, e.g., average glucose, standard deviation, mean amplitude of glucose excursion (MAGE), time in range % (65 and 140 mg/dL), % high (>140 mg/dL), % low (<64 mg/dL), and severe low % (<54mg/dL) and coefficient of variation (CV) and other statistical measures of glucose variability in those with CGM will be reviewed from the RT- CGM device data at baseline and visit 2-4. Blinded CGM values will be obtained at baseline and visit 2 and 3.

Glucose meter: Compliance with fingersticks 4 times a day will be recorded by average number of fingersticks per day. Glucose data including: average glucose, standard deviation, mean amplitude of glucose excursion (MAGE), time in range % (65 and 140 mg/dL), % high (>140 mg/dL), % low (<64mg/dL), and severe low % (<54mg/dL) will also be recorded.

N:Antenatal Ultrasound Markers: estimated fetal weight (in grams and percentile) using Hadlock scale, Biparietal Diameter, Head circumference, abdominal circumference, and femur length. Amniotic Fluid Index.

O: Delivery Outcomes:

Obstetric Outcomes:

- 1.Gestational age at delivery
- 2.Labor status (spontaneous labor, induced labor, no labor). For induced labor include indication for induction
- 3.Mode of delivery (vaginal delivery, cesarean delivery, operative vaginal delivery) including indication for delivery
- 4.Shoulder dystocia: defined as a delivery that requires additional obstetric maneuvers to release the shoulders after gentle downward traction has failed. SD occurs when either the anterior or, less commonly, the posterior fetal shoulder impacts on the maternal symphysis or sacral promontory

Maternal Outcome:

1. Preeclampsia or GHTN
2. Maternal insulin or medication use

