3. Maternal hypoglycemia: symptoms or asymptomatic biochemical hypoglycemia (fingerstick or RT-CGM less than 54 mg/dL (3.0 mmol/L), severe (fingerstick or RT-CGM < 64mg/dl (3.6 mmol/l)
4. Maternal weight gain

Fetal Outcome:

1. Gestational age at delivery
2. Live born or stillbirth

3. Birth weight: (large for gestational age, small for gestational age, macrosomia, birthweight ratio). Large for gestational age: birthweight > 90th centile for gestation using Fenton 2013 growth charts. Small for gestational age: birthweight below the 10th centile using Fenton 2013 growth charts. Macrosomia: birthweight ≥ 4 kg.
4. Birthweight ratio (birthweight adjusted for gestation and gender calculated with the Fenton 2013 web calculator (<http://peditools.org/fenton2013>)).
5. 5- minute Apgar score
6. Respiratory distress
7. Neonatal hypoglycemia: defined as < 4 h of life: < 1.4 mmol/l (30 min after first feed); < 2.2 mmol/l (1 h after subsequent feeds), 4–24 h of life: < 1.9 mmol/l (prefeed); < 2.5 mmol/l (1 h after feed)
8. NICU admission including LOS
9. Birth injury (such as brachial plexus injury)
10. Hypoxic ischemic encephalopathy

P. Risks and Side Effects:

There are various possible risks and side effects that a participant may incur as a result of this study. At the beginning of the study, when participants are administered the informed consent form by research staff, they will be informed that their participation is completely voluntary and will be informed of the risks and benefits. They are free to leave the study at any time and will not be penalized. Potential subjects will also be told that failure to participate in no way affects the usual care they would receive from their OB provider. Only after all questions have been answered, both study staff and the participant will sign and date the consent form.

It is very unlikely that there will be any adverse events

There are possible risks associated with the intervention activities, including the medical device, including:

- a. Less Likely (1% \leq Event Rate < 5%): CGM site infection or tape allergy (<1-2%) (41)
- b. Likely (5% \leq Event Rate < 10%): None
- c. More likely (Event Rate $\geq 10\%$): None

Risk to Participants:

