There is the possibility of bruising, soreness and infection at the sites of needle sticks for blood draws, finger sticks for checking glucose levels and at the insertion sites of the CGM device. All participants will be provided with an emergency number for who to contact if any problems arise.

Continuous Glucose Monitoring Device: Participants may have temporary discomfort at the time of inserting the small filament. This can include bruising or redness of the skin, rare allergy to tape used to keep the device in place, infection at the insertion site, and potential perceived dislike of having a medical device on them for 10 days.

There is the risk of lightheadedness, dizziness and fainting from having blood drawn.

There is the possibility of potential embarrassment answering questionnaires. Participants are told they can leave questions blank if they are uncomfortable answering them.

There is the risk of anxiety because the medical history contains some sensitive questions like alcohol and drug history and questions about previous pregnancies.

There may be confusion about when to test blood sugar which could cause anxiety. Participants will be told to follow the instructions of their provider. Participants will be provided with study contacts for any questions and the study will work in conjunction with the participants' OB provider about blood sugar testing instructions.

There is the risk for participants in RT-CGM in the intervention group missing alerts if the alert notification is turned off.

There is the risk of lack of accuracy of the CGM read outs in the intervention group if the participant takes acetaminophen.

There is the risk for both groups if during insertion of the CGM the insertion wire breaks and becomes lodged under the skin and requires removal.

There are some skin issues that can occur when using the CGM device such as allergic reactions to the device that are localized and can include bruising, rash, soreness, and infection. This skin reaction can also be caused by the tape used to secure the device.

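### Maternal hypoglycemia has no duration or confirmation rule for a CGM event, so single low readings count and unequal sensor wear can bias the arm comparison

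*Combined protocol and SAP*

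**What the plan says.** Section O (Delivery Outcomes, Maternal Outcome 3) gives the first tier as "Maternal hypoglycemia: symptoms or asymptomatic biochemical hypoglycemia (fingerstick or RT-CGM less than 54 mg/dL (3.0 mmol/L". A second tier follows: "severe (fingerstick or RT-CGM < 64mg/dl (3.6 mmol/l". Neither tier states how long a CGM value must stay low, how many readings are needed, or whether a fingerstick must confirm it. No other section supplies such a rule.

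The protocol does recognise that a sensor reading may need checking. Section H tells the RT-CGM arm to "continue fingersticks only when concerned for hypoglycemia and/or inaccuracy of sensor", and at the screening visit gives them a meter, "instructed to use for symptoms of low glucose or if they question the accuracy of the CGM". Neither instruction is tied to the outcome.

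Sensor exposure differs by arm. Section J says: "The intervention group will wear the RT-CGM continuously and change the sensor every 10 days for the duration of the pregnancy". Controls wear a blinded sensor at the start, at 30-32 weeks and at 34-36 weeks, 10 days each time, and otherwise rely on at least four fingersticks a day.

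Section N separately records the percentage of CGM values in two low bands, "low (<64 mg/dL), and severe low % (<54mg/dL". Section H has the RT-CGM arm log at another threshold: "they will be instructed to document any sugars < 60 mg/dl seen by CGM in their log". Section H also says that maternal outcomes come from delivery records and EMR review.

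**The concern.** Three things are left open.

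- **Sensor route.** With no duration rule, a trace reading 58, 53, 57 mg/dL is an event on one value, and so is a trace below 54 for 40 minutes. A momentary error scores the same as a sustained low.
- **Symptom route.** The cut-off sits in a bracket after the second limb and the bracket is never closed. A coder could count symptoms alone, or could read the line as symptomatic or asymptomatic biochemical hypoglycemia with the cut-off governing both.
- **Exposure.** The chance of at least one low reading, true or false, grows with days worn. The RT-CGM arm has several times the sensor days of the controls, and the definition names only fingerstick and RT-CGM, so blinded traces might not be scored at all.

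At stake is a listed safety outcome that also bears on Aim 6 (nocturnal hypoglycemia). RT-CGM could appear to cause lows because it is worn longer, or a real benefit could be hidden or reversed.

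**Working it through.** **The plan's own figure.** There is none for this outcome. The only size figure is 92 participants for HbA1c (section E). A noncentral-F calculation with three measurements, and sphericity and correlation both 0.60, gives 96 at f = 0.14 exactly and 92 at f = 0.143-0.144, so it reproduces within rounding. It has no bearing here.

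**Inputs from the documents.** 50 women per arm. Control sensor exposure is 3 × 10 = 30 days. RT-CGM exposure is 14-22, from the note to Figure 1. The unit is not printed; weeks are assumed from the visit schedule. The lower end, 14 × 7 = 98 days, is used below.

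**Inputs assumed.** The documents give no hypoglycemia rate, sensor-error rate or reading interval. Everything below is an illustration over a range.

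**Step 1: effect of unequal wear.** Let p be the true any-event proportion, q the chance per wear-day of a false single low, and d the days worn.

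P(event) = 1 − (1 − p)(1 − q)^d

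Example with q = 0.5% and p = 10% in both arms:
- RT-CGM: 0.995^98 = 0.612, so 1 − 0.9 × 0.612 = 0.449.
- Control: 0.995^30 = 0.860, so 1 − 0.9 × 0.860 = 0.226.

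The test is a normal-approximation comparison of two proportions, two-sided 0.05, 50 per arm.

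| q per day | False low by 30 / 98 days | No true difference (10% each): control / RT-CGM | Chance of rejecting | True 30% control, 10% RT-CGM: observed difference |
|---|---|---|---|---|
| 0 | 0 / 0% | 10.0 / 10.0% | nominal | −20 points |
| 0.1% | 3 / 9% | 12.7 / 18.4% | 12% | −14 points |
| 0.5% | 14 / 39% | 22.6 / 44.9% | 66% | +5 points |
| 1% | 26 / 63% | 33.4 / 66.4% | 92% | +18 points |

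If blinded traces are not scored (control d = 0), the rejection chances with no true difference become 22%, 98% and about 100%.

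**Step 2: symptom-only events.** If a share s of women in each arm has symptoms without a low value and these count, P = 1 − (1 − p)(1 − s). With s = 20%, control is 1 − 0.7 × 0.8 = 0.44 and RT-CGM is 1 − 0.9 × 0.8 = 0.28. Power for 30% against 10% starts at 0.71 and falls to 0.52, 0.38, 0.29 and 0.17 at s = 10, 20, 30 and 50%. This is dilution, because exposure to it is taken as equal.

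**Step 3: how often one reading misfires.** Simulated traces: readings every 5 minutes, mean 105 mg/dL (between-woman SD 8), within-woman CV 16-20%, autocorrelated glucose and sensor error, cut-off 54 mg/dL. Repeat runs differ by a few points.

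| Sensor error SD | Flagged by one reading, 10 days | Truly below 54, 10 days | Excess |
|---|---|---|---|
| 9% | 39-75% | 12-52% | about 23-32 points |
| 5% | 14-59% | 12-53% | about 2-6 points |

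**Step 4: does a 15-minute rule cure it?** Only partly. At 9% error over 10 days, requiring three consecutive readings flags 16-44%, against 6-28% of women whose true glucose stays below 54 for three readings. With identical glycemia in both arms, the rule flags 51-92% at 98 days against 28-71% at 30 days. For the single-reading rule the figures are 85-100% against 64-93%. The exposure gap therefore needs its own remedy.

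**The case against.** **The symptom limb may be a slip.** The loose wording pairs naturally as symptomatic or asymptomatic, with one cut-off for both. That stands: this limb is an ambiguity to close, not a demonstrated error. A reader might also infer that RT-CGM women can rule out symptoms on screen more easily than controls, which would bias the symptom count. That does not follow. If symptoms alone qualify, a normal reading removes nothing. Controls also have a meter and strips, and nothing bars them from testing when symptomatic.

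**Scoring is not stated.** The plan does not say that the outcome is ever/never or that traces are searched for single values. If events come only from delivery records and EMR review, a momentary 53 may never be counted. This stands, and makes the concern conditional. But section O names RT-CGM as a source and the traces are downloaded, so trace scoring is a fair reading.

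**The risk statement is narrower than it looks.** Section P says "There is the risk of lack of accuracy of the CGM read outs in the intervention group", but the sentence goes on to limit this to acetaminophen use. It does not support a general claim about sensor noise. The section H instructions are the better evidence that inaccuracy was foreseen.

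**The size is fragile.** Changing sensor error from 9% to 5% removes most of the 10-day excess. At 9% error, raising mean glucose to 115 mg/dL lowers the share flagged to 12-46%. This stands.

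**There is a fallback.** The time-low percentages in section N do not saturate with wear and remain usable, but they do not define the event outcome.

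**Conclusion.** The gap is real: no duration or confirmation rule exists for a CGM event, and whether symptoms need a low value is unclear. If traces are scored as any event, false lows inflate the outcome and unequal wear loads more of them on RT-CGM.

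A reader might infer that the outcome simply cannot separate the arms, or that nearly every woman becomes a case. The documents do not support either. Loss of separation needs similar false events in both arms, whereas planned wear is about 98 days or more against 30, so bias is the larger risk. Near-saturation depends on an ever/never rule that the plan does not state and on assumed sensor error.

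The size is not derivable from the documents. On the assumptions shown, the 10-day excess is anywhere from about 2 to 32 points, and a difference where none exists would be declared in 12-92% of trials. The outcome is one of several unpowered maternal outcomes and sample size rests on HbA1c, so this does not threaten the main analysis. It should be settled before events are scored.

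**What to change.** These changes concern outcome scoring only, not clinical care.

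1. Define a CGM event as sensor glucose below the cut-off for at least 15 consecutive minutes. Accept a fingerstick below the cut-off as an alternative, and record which route produced each event, since fingerstick testing also differs by arm.
2. Count symptoms only with a concurrent low value, and classify events as symptomatic or asymptomatic. Report symptoms without a low value separately.
3. Apply the same rule to the controls' blinded traces.
4. Compare arms over matched CGM windows (start of study, 30-32 weeks, 34-36 weeks), or as events per wear-day. Item 1 alone does not remove the exposure gap.
5. Name the data source (CGM trace or meter download) and the unit (any event or rate).

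The cost is outcome wording and a few lines of code on data already downloaded, with no extra visits or participants. The downside is that true lows shorter than 15 minutes are not events, though they remain in the time-low percentages.

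Separately, the order of the 54 and 64 mg/dL tiers in section O runs opposite to section N, and section H logs at 60 mg/dL. These passages must be reconciled.
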